### **Action taken with study treatment**

Any action on study treatment to resolve the AE is to be documented using the categories listed below.

- Drug withdrawn
- Drug interrupted
- Dose reduced
- Dose not changed
- Not applicable

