The regorafenib treatment arm in the CORRECT study included 309 patients < 65 years (307 evaluable for safety), 155 patients 65-74 years and 38 patients  $\geq 75$  years. The OS hazard ratio was 0.72 (95% CI 0.56-0.91) in patients <65 years and 0.86 (95% CI 0.61-1.19) in patients  $\geq 65$  years. The rate of grade  $\geq 3$  adverse events was 52% for patients <65 years, 57% for patients 65-74 years and 66% for patients  $\geq 75$  years. Dose modification was necessary for 76% of patients < 65 years, 73% for patients 65-74 years and 84% for patients  $\geq 75$  years. This underscores the importance of close monitoring and good supportive care for older patients on regorafenib.

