## 4. Study Design

Given 54% grade 3/4 toxicity and required dose modification among 76% of patients in the regorafenib arm (randomized phase III CORRECT trial), we will initiate treatment at a reduced dose of 120mg in this geriatric study population on a similar 3 weeks on/1 week off schedule. Dose escalation to 160mg will be recommended after the first cycle (4 weeks) at the discretion of the treating physician. There is good precedent for starting at reduced doses in similar trials – the FOCUS2 study team utilized 80% starting chemotherapy doses in their study among the elderly with metastatic CRC and dose escalated if tolerated.

Participants will undergo a comprehensive geriatric assessment (CGA) at baseline, at 4 weeks and then every 3 months (+/- 7 days) while on study to assess for any deterioration in geriatric domains (functional status, comorbidities, nutrition, psychological state, social support and cognitive ability). All sites have personnel experienced in performing geriatric assessments and the University of Rochester as the lead site will conduct training to ensure that all sites will conduct the assessments in the same way.

All patients will receive intensive one-on-one education about prevention/management of skin toxicity, diarrhea, fatigue and other toxicities at initiation and follow-up visits (see section 7 & 8 for review of treatment strategies). Starter packs with moisturizing cream (10% urea content), socks and patient-friendly ‘Tips for Skin Care’ will be distributed. On-treatment visits will occur weekly for first two cycles and every 4 weeks after that. Alternate weekly visits may be substituted with a home nursing visit for BP check and symptom evaluation if it is not feasible for patient to attend clinic visits weekly. Pill adherence diaries will be provided to patients and pill counts will be performed at the end of every cycle.

Restaging CT/MRI scans will be completed every 12 weeks (+/- 7 days) (or sooner if treating oncologists suspects progression of disease based on clinical symptoms). Radiographic disease progression is defined by Response Evaluation Criteria in Solid Tumors (RECIST 1.1) (see Appendix A). Subjects will have a Safety Follow-up visit within 30 days after their last dose of study drug or prior to the initiation of another antineoplastic therapy, whichever occurs first. After treatment discontinuation, survival status will be assessed periodically (see Table of Assessments).

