## **7. Treatment[s]**

### **Treatments to be administered**

All patients will receive regorafenib 120mg daily for 3 weeks on and 1 week off with cycle 1. Dose escalation to 160mg will be permitted after the first cycle at the discretion of the treating physician. Subjects will continue study treatment until disease progression or other reasons for removal from treatment (section6).

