### Dose Modification Levels

The starting dose of regorafenib is 120 mg once daily. Study medication will be administered on a 3 weeks on/1 week off schedule [3 weeks out of every 4].

Dose escalation to 160mg is recommended after the first cycle (4 weeks) at the discretion of the treating physician.

Doses will be held or reduced for clinically significant hematologic and non-hematologic toxicities that are related to protocol therapy according to the guidelines shown in the Dose Delays/Dose Modifications tables that follow. Doses held for toxicity will not be made up but will be counted as missed doses. Dose modifications will follow predefined dose levels. Sites may also follow their institutional practice for dose modifications. Missed doses are to be omitted rather than made up. Dose adjustments for hematologic toxicity are based on the blood counts obtained in preparation for the day of treatment.

The modifications of regorafenib will follow the following predefined dose levels:		
Dose level +1	160mg po qd	Four 40-mg tablets of regorafenib
Dose level 0 (starting dose)	120 mg po qd	Three 40-mg tablets of regorafenib
Dose level - 1	80 mg po qd	Two 40-mg tablets of regorafenib
Dose level - 2	40 mg po qd	One 40-mg tablets of regorafenib

If a subject experiences more than one toxicity, dose reduction should be according to the toxicity with the highest grade.

In the case of two or more toxicities of the same grade, the investigator may dose reduce according to that deemed most causally related to study treatment.

If a dose reduction has been performed, intra-subject dose re-escalation can be considered (up to the maximal 160 mg daily dose) at the discretion of the treating physician provided that the toxicity(ies) has resolved to baseline.

The following tables outline dose adjustments for toxicities related to study drug other than diarrhea, hand-foot skin reaction, hypertension and liver function test abnormalities. More information on dose reductions for diarrhea, hand-foot skin reaction, hypertension, and liver function test abnormalities follows Table 7-1.

Table 7-1: Recommended dose modification for toxicities except diarrhea, hand-foot-skin reaction, hypertension and ALT/ST/bilirubin			
NCI-CTCAE v4.0a	Dose Interruption	Dose Modificationb	Dose for Subsequent Cycles
Grade 0-1	Treat on time	No change	No change
Grade 2 c	Treat on time	No change	No change

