## 12. Statistical Methods and Determination of Sample Size

### Statistical and analytical plans

The primary end-point is grade 3-5 toxicity incidence rates. Adverse events will be grouped by system organ class and graded using NCI CTCAE version 4.0. Descriptive statistics (counts and percentages) for grade 3 and 4 toxicity rates and all-grade skin toxicity will be assessed and evaluated in relation to CGA domains.

Relative dose intensity (dose reductions, dose delays, or inability to tolerate treatment) for regorafenib will be calculated. Specific toxicities associated with dose reductions, delays and/or early discontinuation of treatment course will be identified.

Efficacy outcomes will be response rate (RR), disease control rate (DCR), progression-free survival (PFS) and overall survival (OS). Best response will be classified per RECIST criteria into complete response (CR), partial response (PR), stable disease (SD) and progressive disease (PD). Disease control will be the combination of CR + PR + SD. Kaplan-Meier survival curves will be used to estimate median PFS and OS. All statistical tests will be conducted using SAS version 9.2 (SAS Institute Inc).

Analysis of CGA results will be descriptive and will describe mean, median and standard deviations of scores at baseline and at follow up time points. CGA deficits will be captured at baseline and follow up time points. Each domain will be evaluated individually and scores will be compared between baseline and follow up time points. Overall CGA deficits will be examined and proportion of patients who decline in more than 1 domain will be determined for each time point.

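### Neither the AE action-taken list nor the Section 12 toxicity listing captures an adverse event that led the physician to withhold escalation to 160 mg

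*Combined protocol and SAP*

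**What the plan says.** **Dosing.** Section 7, Treatments to be administered, fixes the start: "All patients will receive regorafenib 120mg daily for 3 weeks on and 1 week off with cycle 1". The next step is described in three places. Section 4 says "Dose escalation to 160mg will be recommended after the first cycle (4 weeks) at the discretion of the treating physician", and Section 7, Dose Modification Levels, agrees: "Dose escalation to 160mg is recommended after the first cycle (4 weeks) at the discretion of the treating physician". Section 7, Treatments to be administered, is weaker: "Dose escalation to 160mg will be permitted after the first cycle at the discretion of the treating physician".

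**Recording.** Section 11, Action taken with study treatment, says "Any action on study treatment to resolve the AE is to be documented using the categories listed below". The list is closed: drug withdrawn, drug interrupted, dose reduced, "Dose not changed", and not applicable.

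**Analysis.** Section 12, Statistical and analytical plans, says "Specific toxicities associated with dose reductions, delays and/or early discontinuation of treatment course will be identified". It also plans relative dose intensity, described through reductions, delays and inability to tolerate treatment, without naming the reference dose.

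**The concern.** In a design that starts low and moves up, one way toxicity limits dose is that the upward step is not taken. Both the recording list and the analysis sentence describe dose changes in one direction only: stopping, pausing or lowering. If a physician sees a troublesome event in cycle 1 and keeps the patient at 120 mg, nothing in the visible text records that this event was the reason.

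At stake is the description of how well older patients tolerate this schedule. The plan could report how many patients had doses cut, delayed or stopped, and for which toxicities. It could not report which toxicities kept patients from 160 mg. Section 1 hopes the study will serve as a model for using the drug in geriatric patients, so a reader would reasonably want that answer. The omission makes the dose-tolerability summary look somewhat better than it would with these patients shown.

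**Working it through.** The plan states no figure on this point, so the check is mainly a comparison of passages.

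**Step 1. Which events already lead to a recorded dose action?**
- Table 7-1 (general toxicities): grade 3 and 4 lead to a hold and a one-level reduction. Captured.
- Table 8-2 (hand-foot skin reaction): grade 2 and 3 lead to interruption, and to discontinuation on recurrence. Captured.
- Table 8-3 (hypertension): symptomatic grade 2 and grade 3 lead to a hold, grade 4 to discontinuation. Captured.
- Table 8-4 (transaminases): above 5 x ULN leads to interruption or discontinuation. Captured.

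**Step 2. Which events lead to none?**
- Table 7-1: grade 1, and grade 2 unless several occur together and the oncologist chooses to interrupt.
- Table 8-2: grade 1 hand-foot skin reaction.
- Table 8-3: grade 1 and asymptomatic grade 2 hypertension.
- Table 8-4: transaminases below 5 x ULN, unless above 3 x ULN with bilirubin above 2 x ULN.
- Section 8, Diarrhea, gives no dose table.

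The gap therefore lies mainly in lower-grade events. They are not necessarily trivial: Section 11, Intensity, defines grade 2 as possibly limiting instrumental activities of daily living, a domain the geriatric assessment measures.

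**Step 3. Follow one such patient.** A grade 2 event occurs in cycle 1, there is no hold, and the physician stays at 120 mg for cycle 2 because of it. The likely action code is "Dose not changed", although not applicable is also available and no instruction covers the case. Neither code points to escalation. In Section 12 the patient has no reduction, delay or early stop, so the event is not in the listing.

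**Step 4. Can other data recover it?** Diaries and pill counts (Section 4) show what was taken, not why. There are no escalation criteria beyond physician discretion, so the reason cannot be inferred from AE grades. For a patient who takes every dose at 120 mg, relative dose intensity depends on the unstated reference:
- Reference 120 mg throughout: 120/120 = 100%.
- Reference 160 mg throughout: 120/160 = 75%.
- Reference 120 mg in cycle 1 and 160 mg in cycles 2 to 4: (4 x 120)/(120 + 3 x 160) = 480/600 = 80%.

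Whichever reference applies, a patient kept at 120 mg by toxicity and one kept there by preference get the same value.

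**Step 5. Size.** Patients affected = 60 x share whose escalation is withheld for a toxicity that caused no hold, reduction or stop. The documents do not give that share. Under an assumed range:
- 5%: 60 x 0.05 = 3 patients
- 10%: 60 x 0.10 = 6 patients
- 20%: 60 x 0.20 = 12 patients
- 30%: 60 x 0.30 = 18 patients

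These values illustrate the arithmetic; they are not estimates.

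**The case against.** The strongest reply is that the plan does what it says. Section 12 defines its listing by reductions, delays and early discontinuation, and a listing is not understated for leaving out what lies outside its definition. The action-taken field asks about action to resolve the event, and declining a later increase is arguably not such an action; if the dose stayed at 120 mg, saying it did not change is accurate. Events and grades are recorded in any case, pill counts should show who never reached 160 mg, and inability to tolerate treatment is named under relative dose intensity. If escalation is only permitted, staying at 120 mg is not a departure from the plan.

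Much of this stands, and it rules out stronger conclusions that a reader might infer:
- *That a planned list of dose-limiting toxicities is understated.* No such list is planned. The fault is narrow scope.
- *That a comparison with CORRECT is biased.* Section 1 reports "Dose modification was necessary for 76% of patients < 65 years, 73% for patients 65-74 years and 84% for patients" aged 75 or over, and Section 4 uses 76% to justify the lower start. Section 12 plans no comparison of dose-modification rates; the CORRECT benchmark for sample size is the grade 3-4 toxicity rate.
- *That CORRECT would have recorded a modification for the same event.* The documents do not give its dose-modification rules.
- *That every such event will be coded as unchanged.* That is the likely code, not a stated rule.

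What does not stand is that the information is recoverable. Knowing that a patient had an event and stayed at 120 mg does not show that one caused the other, and inability to tolerate treatment is not tied to escalation or to a particular event. The case report form is not among the documents and may already ask for the reason. If it does, Sections 11 and 12 should say so.

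**Conclusion.** The gap is real and limited. The visible plan neither collects nor reports an adverse event that led to withheld escalation, so it cannot separate non-escalation for toxicity from non-escalation by preference. It affects a secondary description of tolerability, mainly through lower-grade events. The primary endpoint, grade 3-5 incidence, does not use the action-taken field, and the efficacy outcomes do not either.

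The number of patients affected cannot be computed from the documents; the 3 to 18 of 60 above rests wholly on the assumed 5% to 30%. The conclusion assumes that physicians sometimes withhold escalation because of events that trigger no dose action, which is plausible where the decision is discretionary, and that no unseen form records the reason. This is a worthwhile, inexpensive improvement rather than a threat to the trial's main result.

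**What to change.** 1. Section 11, Action taken with study treatment: add the category *escalation withheld because of this AE*.
2. At the end of cycle 1, record once per patient whether the dose was escalated and, if not, the main reason (for example toxicity, with a link to the AE; physician preference; patient preference; treatment stopped). This is needed as well as item 1, because an event may be coded before the escalation decision is made.
3. Section 12: widen the sentence on toxicities affecting dosing to include withheld escalation beside reductions, delays and early discontinuation. Report withheld escalation as its own row, so that the other rows keep their present meaning.
4. Section 12: state the reference dose for relative dose intensity.
5. Reconcile the recommended wording (Section 4; Section 7, Dose Modification Levels) with the permitted wording (Section 7, Treatments to be administered), since it decides whether staying at 120 mg departs from the expected course.

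Items 1 to 4 change no dosing rule, and item 5 asks only that the passages agree. The cost is one form category, one item per patient and small edits to Section 12, with slightly more data entry. The tolerability summary may look slightly less favourable. Items 1 and 2 are best in place before patients reach the end of cycle 1, because later recovery would depend on chart notes.

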#### **Other specific treatment(s) of adverse events**

- None
- Remedial drug therapy

#### **Outcome**

The outcome of the AE is to be documented as follows:

- Recovered/resolved
- Recovering/resolving
- Recovered/resolved with sequelae
- Not recovered/not resolved
- Fatal
- Unknown

#### **Assessments and documentation of adverse events**

Adverse events and grade will be recorded at each follow-up visit. Serious adverse events will be collected and reported from the time patient signs informed consent until the End of Treatment safety follow-up visit. Non-serious adverse events will be collected from the time of first study drug dosing until the End of Treatment safety follow-up visit.

#### **Reporting of serious adverse events**

The definition of serious adverse events (SAEs) is given in Section 11(Definitions).

Each serious adverse event must be followed up until resolution or stabilization, by submission of updated reports to the designated person. An isolated laboratory abnormality that is assigned grade 4, according to CTC definition, is not reportable as an SAE; unless the investigator assesses that the event meets standard ICH criteria for an SAE. CTC grade 4 baseline laboratory abnormalities that are part of the disease profile should not be reported as an SAE, specifically when they are allowed or not excluded by the protocol inclusion/exclusion criteria.

When required, and according to local law and regulations, serious adverse events must be reported to the Ethics Committee and Regulatory Authorities.

All serious adverse events should be reported to the Coordinating Center within 24 hours. The Coordinating Center will then inform the DSMC and Bayer and will report to the RSRB using

the “reportable event” form in the ROSS system. In the event of such an event, the investigator should refer to the Pharmacovigilance section of the contract for reporting procedures.

Non-reportable research events across all sites (including UR site) will be submitted in summary at the time of the Coordinating Center’s Continuing Review.

**The Investigator may report serious adverse drug reactions (SADRs) using either:**

An ADEERS form (Adverse Event Expedited Reporting System) available at <http://ctep.cancer.gov/reporting/adeers.html>

OR

A MedWatch form available at <http://www.fda.gov/medwatch/>

All reports shall be sent electronically to:

## Expected adverse events

Overview listings of frequent adverse events are shown in the most current version of the investigator's brochure (IB) / summary of product characteristics.

If relevant new safety information is identified, the information will be integrated into an update of the IB and distributed to all participating sites.

The expectedness of AEs will be determined by the Coordinating Center and Bayer according to the applicable reference document and according to all local regulations.

## Adverse events of special safety interest

As with any new chemical entity, there is always potential for unexpected adverse events, including hypersensitivity reactions.

Based on data studies with regorafenib and from current knowledge of the pharmacological properties of other small molecule tyrosine kinase inhibitors in this drug class, as soon as there is reasonable suspicion of any of the following AEs, the investigator should immediately notify the Coordinating Center as outlined in Section 11 (Reporting of Serious Adverse Events).

Reportable adverse events include:

- Acute renal failure (NCI-CTCAE version 4.0  $\geq$  grade 3) or severe proteinuria (NCI-CTCAE version 4.0  $\geq$  grade 3)
- Interstitial lung disease
- Acute cardiac failure
- Clinically significant bleeding (NCI-CTCAE version 4.0  $\geq$  grade 3)
- Stevens-Johnson Syndrome and erythema multiforme
- Hepatic failure
- Reversible posterior leukoencephalopathy syndrome
- Gastrointestinal perforation or fistula

## Pregnancies

The investigator must report to the Coordinating Center any pregnancy occurring in a study subject's partner during the subject's participation in this study. The report should be submitted within the same timelines as an SAE, although a pregnancy per se is not considered an SAE.

For the pregnancy of a study subject's partner, all efforts should be made to obtain similar information on course and outcome, subject to the partner's consent.

The MedWatch form should be used to submit this information and is available at <http://www.fda.gov/medwatch/>

## Further safety

### Progressive disease

If progressive disease leads to signs and symptoms that meet the criteria for an SAE (i.e., hospitalization, disability, death, or important medical event), the signs and symptoms should be reported as an SAE and not the underlying progressive disease.

### Death

If any subject dies during the trial or within 30 days of the end-of-treatment visit, the investigator will inform the Coordinating Center and will record the cause of death in detail (using the SAE Form) within 24 hours.

## Appropriateness of procedures / measurements

The assessments described in the previous sections are widely used and generally recognized as reliable, accurate, and relevant for determining the safety and efficacy of therapies in this disease.

## Safety Analyses

The Data Safety Monitoring Committee (DSMC) at the James P. Wilmot Cancer of the University of Rochester will review and monitor toxicity and accrual data from this trial. The committee is composed of clinical specialists with experience in oncology who have no direct relationship with the study. Information that raises any questions about participant safety will be addressed with the investigators and study team.

The DSMC will provide oversight of study progress and safety by review of accrual and adverse event data at semi-annual meetings or more frequently if concerns arise. Any adverse effects requiring expedited review per protocol will be submitted to the chair of this committee for determination as to whether further action is required. This committee will meet after 6 patients have been enrolled and received at least one cycle of therapy. If >3 of these first 6 patients have delays in treatment administration due to toxicity, accrual will be held pending review and discussion with the investigators.

The study team will record and monitor adverse event rates utilizing the University of Rochester Cancer Center Clinical Trial database. If the study has two or more of the same SAEs reported in a month or more than six of the same SAEs in six months, the DSMC will review a summary of SAEs, discuss events with study investigators and conduct a detailed review. The DSMC will determine if further action is required. A copy of the DSMC reports will always be sent to all participating sites for review and submission to their local IRB.

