## **6. Withdrawal of Subjects from Study**

### **Withdrawal**

Subjects **must be withdrawn from the trial** (treatment and procedures) for the following reasons:

- Subject withdraws consent from study treatment and study procedures. A subject must be removed from the trial at his/her own request or at the request of his/her legally acceptable representative. At any time during the trial and without giving reasons, a subject may decline to participate further. The subject will not suffer any disadvantage as a result.
- If, in the investigator's opinion, continuation of the trial would be harmful to the subject's well-being.
- Subject is lost to follow-up.
- Death.

Subjects **may be** withdrawn from the study for the following reasons:

- The subject is non-compliant with study drug, trial procedures, or both; including the use of anti-cancer therapy not prescribed by the study protocol.
- Severe allergic reaction to regorafenib (such as exfoliative erythroderma or Grade 3 or 4 hypersensitivity reaction).
- The development of a second cancer.

- Development of an intercurrent illness or situation which would, in the judgment of the investigator, significantly affect assessments of clinical status and trial endpoints.
- Deterioration of ECOG performance status to 4.
- Use of illicit drugs or other substances that may, in the opinion of the investigator, have a reasonable chance of contributing to toxicity or otherwise skewing trial result.

In all cases, the reason for withdrawal must be recorded in the CRF and in the subject's medical records.

Details for the premature termination of the study as a whole (or components thereof [e.g. centers, dose levels]) are provided in Section 13. Premature Termination of the Study).

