
3
 
Systolic BP ≥ 160 mmHg or diastolic BP ≥ 100 mmHg OR More than one drug or more intensive therapy than previously used indicated
	
Treat with the aim to achieve diastolic BP ≤ 90 mm Hg: Start anti-hypertensive medication
 
AND/OR Increase current anti-hypertensive medication
 
AND/OR Add additional anti-hypertensive medications.
	
 
• Hold regorafenib until diastolic BP ≤ 90 mm Hg, and if symptomatic, until symptoms resolve.a
 
• When regorafenib is restarted, continue at the same dose level.
 
• If BP is not controlled with the addition of new or more intensive therapy, reduce by 1 dose level.b
 
• If Grade 3 hypertension recurs despite dose reduction and antihypertensive therapy, reduce another dose level.c
 

4
 
Life-threatening consequences (eg, malignant hypertension, transient or permanent neurologic deficit, hypertensive crisis)
	Per institutional guidelines	Discontinue therapy

a. Patients requiring a delay of >4 weeks should go off protocol therapy
 
b. If BP remains controlled for at least one cycle, dose re-escalation permitted per investigator's discretion.
 
c. Patients requiring >2 dose reductions should go off protocol therapy.
		

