### Liver Function Abnormalities

For patients with observed worsening of liver tests considered related to regorafenib (i.e. where no alternative cause is evident, such as post-hepatic cholestasis or disease progression), the dose modification and monitoring advice in Table 8-5 should be followed.

Regorafenib is a UGT1A1 inhibitor. Mild, indirect (unconjugated) hyperbilirubinemia may occur in patients with Gilbert’s syndrome.

Table 8-4: Dose Modification/interruption for alanine aminotransferase and/or aspartate aminotransferase increases related to study drug

Increases in ASL/ALT (per NCI-CTCAE v 4.0)	1st Occurrence	Restart	Recurrence
AST and/or ALT < 5 X ULN (<Grade 3)	Continue dosing, with weekly monitoring of liver function until transaminases return to < 3 X ULN (< Grade 1) or baseline.		
ALT and/or AST > 5 X ULN (> Grade 3)	Interrupt dosing, with weekly monitoring until transaminases return to < 3 X ULN or baseline.	If the potential benefit of reinitiating regorafenib is considered to outweigh the risk of hepatotoxicity: reduce 1 dose level and measure transaminases weekly for at least 4 weeks.	Discontinue
ALT and/or AST > 20 X ULN (> Grade 4)	Discontinue		
ALT and/or AST > 3 X ULN (> Grade 2) with concurrent bilirubin > 2 X ULN	Discontinue treatment and measure transaminases weekly until resolution. Exception: subjects with Gilbert's syndrome who develop elevated transaminases should be managed as per the recommendations outlined above for ALT/AST elevations.		

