## 11. Safety

All subjects who receive at least one dose of study treatment will be valid for the safety analysis.

All observations pertinent to the safety of the study treatment will be recorded and included in the final report.

Safety variables include the following: AEs, laboratory changes (complete blood counts, electrolytes, chemistry, and coagulation) and changes in vital signs (blood pressure, heart rate, respiratory rate, and temperature).

All AEs whether considered drug-related or not, will be reported in with a diagnosis, start/stop dates, action taken, whether treatment was discontinued, any corrective measures taken, outcome, and other possible causes. For all events, the relationship to treatment and the intensity of the event will be determined by the investigator.

This trial will use the NCI-CTCAE v4.0 criteria for assessment of toxicity and SAE reporting with regard to toxicity grade.

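### The only automatic accrual hold counts treatment delays and does not name permanent discontinuation or toxic death, and the six patients it counts are not clearly defined

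*Combined protocol and SAP*

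**What the plan says.** Section 11, Safety Analyses, sets an early look by the DSMC: "This committee will meet after 6 patients have been enrolled and received at least one cycle of therapy". The rule attached to it is "If >3 of these first 6 patients have delays in treatment administration due to toxicity, accrual will be held pending review". No other rule in the protocol pauses accrual automatically. Repeated SAEs lead to a DSMC review, expedited events go to the committee chair, and Section 13 allows the study to be ended for safety reasons. Each of these depends on someone's decision.

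The protocol treats a delay and a stop as different things. Section 12 says "Specific toxicities associated with dose reductions, delays and/or early discontinuation of treatment course will be identified". Section 11, under the heading on action taken, says "Any action on study treatment to resolve the AE is to be documented using the categories listed below", and the list that follows has separate entries for drug withdrawn and drug interrupted. The safety population is defined by dosing, not by completing a cycle: "All subjects who receive at least one dose of study treatment will be valid for the safety analysis".

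Some paths in Section 8 go to discontinuation with no interruption step:

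- Grade 4 hypertension in Table 8-3, described as "Life-threatening consequences (eg, malignant hypertension, transient or permanent neurologic deficit, hypertensive crisis".
- ALT or AST above 20 x ULN in Table 8-4.
- ALT or AST above 3 x ULN with bilirubin above 2 x ULN in Table 8-4: "Discontinue treatment and measure transaminases weekly until resolution" (with an exception for Gilbert's syndrome).

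The primary endpoint in Section 12 is grade 3-5 toxicity, so toxic death is part of it.

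**The concern.** An early safety rule should become more likely to act as the more serious consequences of toxicity accumulate. Here a patient who is permanently stopped, or who dies of toxicity, without first having a delay occupies one of the six places and contributes no event. The rule is then harder to trigger than if that patient had merely been interrupted.

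It is also unclear who the six are. The mention of one cycle may only set the date of the meeting, or it may define membership. Under the second reading a patient lost to toxicity in cycle 1 is not among the six at all. Either way that patient adds nothing to the count.

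The stake is whether enrolment of older adults continues by default while the early toxicity data are discussed.

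**Working it through.** **Inputs.** The threshold is more than 3 of 6, so at least 4 (Safety Analyses). Planned accrual is 3-4 patients per month to a total of 60 (Section 12, Determination of sample size). Treatment starts within 14 days of registration and a cycle is 28 days (Section 7, Study Treatment). The documents state no operating characteristic for the rule and no rate of delays or of undelayed stops, so there is no plan figure to reproduce.

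**Step 1: counting bound, if the patients are among the six.** Let k be the number who stop or die of toxicity with no earlier delay. At most 6 - k can have a delay, and 4 are needed.

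| k | Most delays possible | Share of the others that must be delayed | Can the hold fire? |
|---|---|---|---|
| 0 | 6 | 4/6 = 67% | yes |
| 1 | 5 | 4/5 = 80% | yes |
| 2 | 4 | 4/4 = 100% | yes |
| 3 or more | 3 or fewer | not attainable | no |

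Three undelayed stops or deaths plus three delays means that all six had treatment-limiting toxicity, with no automatic hold. Four delays and two patients without toxicity do trigger it.

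**Step 2: the other reading of the six.** If only patients who received a cycle are counted, cycle-1 losses are passed over and later patients fill the six. The bound in step 1 then does not apply to those losses, and the hold can still fire at 4 of 6, but only on other patients. For example, three losses in cycle 1 and three delays among the next six gives 3 + 3 = 6 of 9 treated patients with treatment-limiting toxicity and no hold.

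**Step 3: chance of a hold, as written and with the wider count.** Let d be an assumed delay probability for each of the other 6 - k patients. As written the chance is P(Bin(6 - k, d) ≥ 4). If stops and deaths also count, it is P(Bin(6 - k, d) ≥ 4 - k).

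| k | d = 0.3 | d = 0.5 | d = 0.7 |
|---|---|---|---|
| 0 | 7%, unchanged | 34%, unchanged | 74%, unchanged |
| 1 | 3% to 16% | 19% to 50% | 53% to 84% |
| 2 | 0.8% to 35% | 6% to 69% | 24% to 92% |
| 3 | 0 to 66% | 0 to 88% | 0 to 97% |

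**Step 4: how often k reaches 3.** For an assumed per-patient probability q of an undelayed stop or toxic death, P(Bin(6, q) ≥ 3) is 0.2% at q = 5%, 1.6% at 10% and 10% at 20%.

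**Step 5: where accrual stands at the look.** This assumes even accrual. Cycle 1 takes 28 days (0.92 months), or 42 days (1.38 months) if treatment starts 14 days after registration. Enrolment when the sixth patient finishes cycle 1 is between 6 + 3 x 0.92 = 8.8 and 6 + 4 x 1.38 = 11.5. That is about 9-12 patients, with roughly 48-51 of 60 still to come.

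**The case against.** The strongest reply is that the gap is narrow and well backed up.

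- **Most toxicity does count.** Table 7-1 holds drug for Grade 3 and 4 events, and the hand-foot, hypertension and liver tables mostly interrupt first. A stop that follows an interruption, such as failure to recover within four weeks, has already scored as a delay. This stands. A reader might infer that the rule generally works backwards as toxicity worsens. The documents support that only for the undelayed subset.
- **The direct-stop list is short.** Table 8-4 already interrupts above 5 x ULN, and the Table of Assessments shows laboratory tests in each weekly column of the first cycles. A stop above 20 x ULN with no earlier interruption therefore needs a jump between tests. A reader might add severe allergic reaction, but Section 6 makes withdrawal optional there, and Table 7-1 generally holds drug for Grade 3-4 events. It is not a sound example.
- **Three of six is uncommon.** Section 1 gives grade 3+ rates in CORRECT of 7% for hypertension and 8% for hyperbilirubinemia. Neither is the rate of an undelayed stop, and only the Grade 4 part of the hypertension figure goes straight to discontinuation. The rule is weakened at one or two such patients, but the impossible case is rare on most assumptions.
- **Oversight continues.** The DSMC meets on these patients whether or not the hold fires. SAEs and deaths are reported within 24 hours, and the study can be ended under Section 13. This stands, and a reader who infers that toxic deaths would go unnoticed is mistaken. These routes are discretionary, however. The repeated-SAE review needs the same event twice in a month or more than six times in six months. By default an isolated Grade 4 laboratory abnormality is not reportable as an SAE, so a laboratory-driven stop may not reach that review.

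It can also be said that delay was meant loosely, to include stopping. Sections 11 and 12 list the two separately, so the wording does not secure that meaning.

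**Conclusion.** The point holds on the literal wording, with moderate confidence. The automatic hold omits permanent discontinuation and death due to toxicity, and an undelayed case of either adds nothing to the count.

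The size depends on who the six are. If such patients are among them, the requirement on the others rises from 67% to 80% and then 100%, and from three onward the hold cannot fire. If receipt of a cycle defines the six, patients lost in cycle 1 fall outside the count and the hold can fire only on others. A flat statement that three toxic stops or deaths disable the rule is therefore too strong, because it assumes the first reading.

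No probability is claimed for the trial itself, since the documents give no rate of undelayed stops. The percentages in steps 3 and 4 rest on assumed rates. Detection and DSMC authority are intact. What is lost is the default pause, and further enrolment at 3-4 patients per month follows only if the DSMC does not act. A correction is worth making because it is cheap and because this is a trial whose primary endpoint is toxicity.

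**What to change.** Replace the counted event and define the six, leaving the consequence (a pause for review and discussion) as it is:

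- **Trigger:** *more than 3 of the first 6 treated patients have a treatment delay, permanent discontinuation or death due to toxicity, including during cycle 1.*
- **The six:** the first six patients to receive a dose of study drug, in line with the safety population, assessed once each has completed cycle 1 or stopped earlier.
- **Threshold:** the DSMC should confirm that more than 3 still suits the wider count.

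No new data are needed. Section 11 already records drug withdrawn, drug interrupted and fatal outcome for each adverse event.

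The cost is that the hold may fire more often or earlier. Comparing P(Bin(6, d) ≥ 4) with P(Bin(6, d + q) ≥ 4), at an assumed delay probability of 0.3 the chance of a hold rises from 7% to 12% if undelayed stops or deaths occur at 5%, and to 18% at 10%. At a delay probability of 0.5 it rises from 34% to 44% and 54%. If no such events occur among the six, nothing changes. The hold remains a pause pending review and does not close the trial.
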